7.3. Followup for Serious Negative Reactions

Adverse Events, Serious Adverse Events, Unanticipated Problems, and Deaths have specific reporting procedures.

As part of NH staff training, instructions will be given as to what constitutes an AE / SAE / UP. NH staff will be instructed to stop the music if an event occurs in which resident distress seems to result from the music (AE). NH staff are already trained in fall response (SAE). The NH staff should report any AE / SAE / UP to his/her immediate supervisor as soon as possible, but not exceeding 4 hours after the event. If deemed by the supervisor to be a true AE / SAE / UP, the NH supervisor will complete a *Nursing Home Event Reporting Form*, which will be submitted to the research project director via email within 24 hours of the event. The project director will report the event to the PI via email or telephone immediately upon becoming aware of the event.

Similarly, as part of the observer training, data collectors will be given instructions as to what constitutes an AE / SAE / UP. Data collectors will be instructed to terminate an observation if an event occurs in which resident distress seems to result from being observed (AE). Data collectors will report events to the NH supervisor as soon as possible, but not exceeding 4 hours after the event. If deemed by the supervisor to be a true AE / SAE / UP, the NH supervisor will complete a *Nursing Home Event Reporting Form*, which will be submitted to the research project director via email within 24 hours of the event. The project director will report the event to the PI via email or telephone immediately upon becoming aware of the event.

Upon receipt of the *Nursing Home Event Reporting Form*, the project director and [name] will contact the NH supervisor and complete the *Event Verification Form*. [name] is a co-investigator on the project and a board-certified geriatrician with NH medical experience. Specifically, the project director and [name] will review the details of the event with the NH supervisor, confirm that the event meets criteria for a true AE / SAE / UP, and classify the severity, expectedness, and relatedness of the event.

During verification, if it is determined that the event does not meet the criteria for a true AE/ SAE/ UP, the *Nursing Home Event Reporting Form* and the *Event Verification Form* will be retained by the study team, and no further action will be taken.

During verification, if it is determined that the event is a true AE (and not a SAE or UP), the *Nursing Home Event Reporting Form* and the *Event Verification Form* will be retained for quarterly reporting of AEs to the Data Safety Monitoring Board (DSMB), the NIA Program Officer, and the IRB. A summary of AEs will be included in the semi-annual DSMB report.

During verification, if it is determined that the event is a true SAE, the PI will notify the DSMB, the NIA Program Officer, and the IRB within 24 hours of the research team becoming aware of the event (within 48 hours of the event occurring). The *Event Verification Form* will also be used to capture the follow-up status of a resident who has experienced a SAE. The *Nursing Home Event Reporting Form* and the *Event Verification Form* will be retained and a summary of SAEs will be included in the semi-annual DSMB report.

During verification, if it is determined that the event is a true UP, the PI will notify the DSMB, the NIA Program Officer, the Office for Human Research Protections, and the IRB within 24 hours of the research team becoming aware of the event (within 48 hours of the event occurring). The *Event Verification Form* will also be used to capture the follow-up status of a resident who has experienced a UP. The *Nursing Home Event Reporting Form* and the *Event Verification Form* will be retained and a summary of UPs will be included in the semi-annual DSMB report.

We will receive information on deaths occurring within the nursing home monthly, based on administrative data sent from participating NH corporations to Brown University. Deaths among residents exposed to the intervention will be reported within 24 hours of study's knowledge of death. The report of death will be submitted via email to NIA Program Officer and to the DSMB Chair.

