Certification and Survey Provider Enhanced Reporting (CASPER): CASPER are publicly-available data from the Medicare/Medicaid certification and inspection process that all NHs undergo. Brown investigators have assembled a three-decade data panel on all certified U.S. facilities including data on ownership, size, staffing, services, patient acuity, and quality inspection results.(81, 82)

Primary Data

Primary data collection tools can be found in Appendices B-H. These data will be collected by independent data collectors during three site visits (baseline, four, and eight months).

iPod Metadata: The iPod shuffle retains limited data about use. Information about the songs played (e.g., artist, album, track title, duration of track, genre) and the number of times a song is played are available and will be downloaded.

Staff Interviews: the RAs will interview the NH caregiver most familiar with the resident using the Cohen Mansfield Agitation Inventory (CMAI), a validated 29-item tool for measuring agitation in people with ADRD living in NHs.(83, 84) We will use the CMAI to assess the frequency and severity of eligible residents' behaviors over the previous week.

Resident Observation (Trial 1 Only): The Agitated Behaviors Mapping Instrument (ABMI) will be used to observe resident behaviors at the point of intervention. Using independent, trained observers, we will observe

the frequency of residents' agitated behaviors over short intervals, when they are using and not using the M&M intervention. We will also use the Lawton Observed Emotion Rating Scale (OERS),(85) which was designed to measure pleasure, anger, anxiety/fear, sadness, and general alertness. Reactions to music will be captured, when observations include the use of M&M.

Implementation Observation Checklist: The Implementation Observation Checklist is completed by data collectors while on-site. It describes adherence to specific aspects of the study protocol (e.g., are the playlists individualized, are the iPods labeled, are frontline staff involved in delivering intervention to residents, etc).

Key Informant Interviews: Key informant interviews with the administrator and nursing lead in each intervention facility will be completed by Brown research team members at 4- and 8-months (mid- and full-implementation). These interviews will identify facilitators, barriers, and best-practices related to implementing the M&M program, and feedback on corporate trainings.

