7.2. Serious Negative Reactions and Serious Adverse Events

Please refer to the Data Safety and Monitoring Plan and Data Safety Monitoring Board Charter for complete safety assessment information.

Adverse Events: An adverse event (AE) is any untoward or unfavorable medical occurrence in a human study participant, including any abnormal sign (e.g. abnormal physical exam or laboratory finding), symptom, or disease, temporally associated with the participants' involvement in the research, whether or not considered related to participation in the research. The potential AEs that could occur during this trial are: distress or strong negative emotional reactions in response to listening to the music delivered via the M&M intervention; and distress or strong negative emotional reactions in response to being observed (Trial 1 Only). Distress or strong negative emotional reactions to the music may include screaming / calling out, crying (not always a negative response), or attempting to remove headphones. Distress or strong negative emotional reactions to being observed may include screaming or becoming agitated / aggressive. Distress resulting from the music and the distress of being observed by a data collector would be classified as mild because the distress is easily tolerated and/or remediated, requires no medical evaluation, and has signs and symptoms that are transient. An immediate, negative reaction to the music would fit the study relatedness category "Definitely Related." A negative reaction to being observed would fit the study relatedness category "Possibly Related." as it will likely be difficult to precisely determine the origins of behaviors and reactions in residents with advanced dementia, and it is unclear the extent to which the resident might be aware that s/he is being observed. AEs resulting from negative reactions to the music are expected but likely rare. AEs resulting from negative reactions to the data collectors are not expected.

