7.4. Protection Against Risks

Procedures to minimize against risks include: training NH staff on how to choose appropriate candidates to receive the intervention and how to deliver the intervention to minimize risk of negative reactions; training data collectors to conduct resident observations as unobtrusively as possible; and extensive data safety protocols.

Training NHs: There are several levels of ongoing training and monitoring. NH corporate leadership will receive a two-day initial training on how to help their participating NHs select residents who are likely to respond positively to the intervention. During this training, leadership will also be taught the best way to approach the residents with the music, in order to minimize negative reactions related to startling them. For example, the training details how to initially hold the headphones away from the resident's ears to allow the resident to hear and get used to the music before experiencing the sensory pressure of the headphones. Corporate leadership will then repeat this training with each of their participating NHs before the intervention begins. Once the intervention begins, monthly phone calls will be made to NH staff by corporate leadership and Brown University staff in order to reinforce these best practices for minimizing negative reactions and to monitor for any events that have not been otherwise reported. In addition, corporate leadership will visit each site twice during the study to make sure the intervention is being administered consistent with best practices.

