Mood. The MDS includes the Patient Health Questionnaire (PHQ-9) a validated measure of depressed mood asked of the residents or if unable to respond to the interview, rated by staff.(96)

9.4.3. Process Measures for Implementation Analysis:

We will adopt five distinct approaches to assessing implementation: 1) a user-defined assessment (UDA) by which potentially eligible residents are assessed for their ability to listen to music, their music preferences, and the results of the initial trial of the iPod; 2) iPod metadata about each song that is played, including a count of the times played (and therefore the sum of all plays per unit time); 3) documentation of NH staff participation and attendance in M&M training and monthly corporation calls; 4) key informant interviews of NH staff during and after implementation; and 5) implementation observation checklist, completed on-site by data collectors, to

describe adherence to specific aspects of the study protocol (e.g., are the playlists individualized, are the iPods labeled, etc). Table 4 describes the relationship between primary and secondary data sources and study outcomes.

Me 4. Relationship of Data Sources to S	luuy Oulcom	63				
	Agitation / Aggression	Mood	Antipsychotic Mediation	Anxiolytic Medications	Antidepressant Medications	Implementation
Secondary Data						
Minimum Data Set	X	Х	Х	Х	Х	
User Defined Assessment						Х
Medication Order Records			Х	Х	Х	
Primary data						
Staff Interview	X					
Resident Observation	X	Х				
iPod Metadata						Х
Key Informant Interview						Х
Implementation observation						Х

Table 4 Deletionabi	n of Doto Sourc	an to Stud	/ Outcomes
Table 4. Relationshi	p of Data Sourc	es lo siud	Vulcomes

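### Section 7.3 lets the nursing home supervisor dismiss a reported event before any study reviewer sees it, with no described record and only a loosely connected monthly call as backstop

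*Combined protocol and SAP*

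**What the plan says.** Section 7.3 describes two entry points. For home staff: "The NH staff should report any AE / SAE / UP to his/her immediate supervisor as soon as possible, but not exceeding 4 hours" after the event. For the study's observers: "Data collectors will report events to the NH supervisor as soon as possible, but not exceeding 4 hours after the event". Both paragraphs then continue identically: "If deemed by the supervisor to be a true AE / SAE / UP, the NH supervisor will complete a" Nursing Home Event Reporting Form, which goes by email to the project director within 24 hours of the event.

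On receipt of that form, the project director and a clinician contact the supervisor and complete the Event Verification Form. The clinician "is a co-investigator on the project and a board-certified geriatrician with NH medical experience". These two confirm whether the event is a true one and classify its severity, expectedness and relatedness. AEs then go into periodic reports. SAEs and UPs are notified within 24 hours of the research team's awareness and within 48 hours of occurrence.

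Section 7.4 adds monthly calls to home staff by corporate leadership and Brown staff, partly "to monitor for any events that have not been otherwise reported". Deaths come through monthly administrative data from the corporations (7.3). Section 7.2 refers the reader to the Data Safety and Monitoring Plan and the DSMB Charter for the full safety procedures.

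**The concern.** There are two screens in series, and the less qualified one comes first. On the form route the project director and geriatrician can remove an event that the supervisor forwarded. They cannot restore one that the supervisor dismissed, because nothing reaches them. The supervisor works for the home that is delivering the programme.

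This matters more than usual here because other safeguards are few. Individual consent is waived (7.1), and there are no stopping rules, on the ground that serious reactions will be extremely rare (9.3). The event count is the main evidence by which the DSMB could check that premise. If the count depends on what supervisors choose to forward, and dismissals are not recorded, a low count cannot be distinguished from low forwarding.

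**Working it through.** No event rate or forwarding rate is stated, so there is no plan figure to reproduce. The check traces each route by which an event can reach the study team.

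1. **Form, event seen by home staff (7.3).** Staff to supervisor within 4 hours; form only if the supervisor deems the event true; verification on receipt. The supervisor can stop it.
2. **Form, event seen by a data collector (7.3).** The same path and condition. Section 7.3 gives the data collector no direct line to the project director. The supervisor can stop it.
3. **Monthly call (7.4).** The text does not make this depend on the supervisor. It is addressed to home staff, does not expressly cover events that were reported and then dismissed, and has no stated step leading to the Event Verification Form or the DSMB.
4. **Deaths (7.3).** Administrative data, independent of the supervisor.
5. **Weekly calls with data collectors in data-collection months (10.1).** Contact exists, but event reporting is not a stated purpose.

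**Records.** An event rejected at verification leaves two forms, both retained by the study team (7.3). For an event rejected by the supervisor, no record is described. Only the second kind of rejection can therefore be audited.

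**Who decides what.** A UP under 7.2 must be unexpected, at least possibly related, and indicative of greater risk. To deem an event a true UP, the supervisor must already judge expectedness and relatedness, which 7.3 assigns to the project director and geriatrician. An AE under 7.2 needs no relation to the research at all, yet a supervisor may well set aside a fall as routine in residents who, as 7.2 notes, fall often anyway.

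**Timing of the backstop.** The limit is 48 hours = 2 days from occurrence. Assume calls 30 days apart and events spread evenly between them. The share of events occurring within 2 days before a call is 2/30 = 6.7% (2/31 = 6.5% to 2/28 = 7.1% for other month lengths). This is an upper bound on what the call alone could bring in on time, since verification must still follow.

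**Size of the undercount.** Let s be the share of true events that supervisors forward, and c the share of the remainder that the calls recover and pass to verification. Then

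share missed = (1 − s)(1 − c).

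This ranges from 0 (if s = 1 or c = 1) to 1 − s (if c = 0). The documents give neither s nor c. Without a record of dismissals, the trial as described could not estimate them either.

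**The case against.** **Other routes exist.** A reader might infer that dismissed events never reach the study, or that the DSMB counts are biased downward by design. The documents do not support either. The monthly call looks for unreported events, Brown staff take part in it, and deaths bypass the supervisor. Late or uncertain recovery is not the same as none, so the defensible claim is a risk of undercounting of unknown size.

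**Attribution of music reactions.** It is also tempting to cite 7.2, where "it will likely be difficult to precisely determine the origins of behaviors and reactions in residents with advanced dementia", as showing that supervisors will struggle with music reactions. That clause explains why a reaction to being observed is rated possibly related. An immediate negative reaction to the music is classed as definitely related. The clause does not help the argument for the main harm of interest.

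**Trial 1 only.** Resident observation (6.1) and onsite data collection (10.1) are labelled Trial 1 only, and 9.2 says that the first trial is complete. The data-collector part is therefore largely retrospective. The staff route applies to both trials.

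**Documents not seen.** The Data Safety and Monitoring Plan and the DSMB Charter could contain a further route. The user-defined assessment records "the results of the initial trial of the iPod" (9.4.3), and for Trial 1 observations, "Reactions to music will be captured, when observations include the use of M&M" (6.1). This protocol does not describe either as feeding the safety reports, but that is silence, not proof. The fields of the assessment are not visible, so it is not established that it records negative reactions.

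**Workload and stakes.** Section 1 says that over 80% of people with dementia show behavioural symptoms, and the AE definition is broad. The IRB agreed that risk is minimal, and the named music reaction is classed as mild. These points stand as reasons for proportion. They do not defeat a change limited to events that trained staff already report upward as an AE, SAE or UP.

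**Conclusion.** The point holds for the form route. Section 7.3 itself, by its stated rule, lets someone outside the study team remove events that the qualified reviewers then have no stated means to restore. Dismissals leave no described record, and the 7.4 call has no defined link to verification. Under the even-timing assumption, that call could bring in at most about 7% of otherwise missed events within 48 hours.

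The consequence is a possible undercount of AEs, SAEs and UPs in the DSMB reports. Its size is unknown, and could be zero if supervisors forward everything or the calls recover everything. Deaths are not affected. The conclusion assumes that the Data Safety and Monitoring Plan adds no independent route; if it does, 7.3 should cite it. This is a worthwhile, inexpensive improvement to safety ascertainment and does not touch the primary efficacy analysis.

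**What to change.** - **Section 7.3, staff route:** send every event that staff report to the supervisor as an AE, SAE or UP on the existing Nursing Home Event Reporting Form within the existing 24 hours. Record the supervisor's opinion as a field on the form. Leave the decision on whether the event is a true one to the project director and geriatrician on the Event Verification Form.
- **Section 7.4:** state that an event found on a monthly call goes to the same Event Verification Form, with the dates of occurrence and discovery recorded.
- **Where data collectors are on site:** copy their reports to the project director at the same time as to the supervisor.
- **Optional:** if the user-defined assessment does record negative reactions, tabulate them with denominators in the DSMB report. The denominator would be at most 27 homes × 15 residents = 405 first music trials in each trial, if every planned resident is tried.

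The cost is a wording change and more forms to verify, some of them false alarms. The number of extra forms cannot be estimated from the documents. The forms, the 24-hour deadline and the people who verify events are already in place.

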7.4. Protection Against Risks

Procedures to minimize against risks include: training NH staff on how to choose appropriate candidates to receive the intervention and how to deliver the intervention to minimize risk of negative reactions; training data collectors to conduct resident observations as unobtrusively as possible; and extensive data safety protocols.

Training NHs: There are several levels of ongoing training and monitoring. NH corporate leadership will receive a two-day initial training on how to help their participating NHs select residents who are likely to respond positively to the intervention. During this training, leadership will also be taught the best way to approach the residents with the music, in order to minimize negative reactions related to startling them. For example, the training details how to initially hold the headphones away from the resident's ears to allow the resident to hear and get used to the music before experiencing the sensory pressure of the headphones. Corporate leadership will then repeat this training with each of their participating NHs before the intervention begins. Once the intervention begins, monthly phone calls will be made to NH staff by corporate leadership and Brown University staff in order to reinforce these best practices for minimizing negative reactions and to monitor for any events that have not been otherwise reported. In addition, corporate leadership will visit each site twice during the study to make sure the intervention is being administered consistent with best practices.

Training Data Collectors: Data collectors will attend a three-day training at Brown University before the start of the intervention. During this training, data collectors will visit a NH to become familiar with the setting and to practice conducting observations unobtrusively. During the actual study, a maximum of four observations will be conducted for each resident during a data collector visit, with two data collector visits per resident over the course of the study. Each observation will be a maximum of five minutes in duration. The data collector will neither be left alone with the resident nor interact directly with the resident. Whenever possible, the observation will be done when the resident is in a common area, but this may not always be feasible. If the observation is done while the resident is in his or her room, the data collector will remain outside of the room and observe as discreetly as possible through an open door. The goal is for the data collector to be as inconspicuous as possible. This protocol has been approved by the Brown University IRB.

